Effectiveness Endpoints	
 • Unstimulated salivary flow rate (USFR) (Assessor) at each study visit; • Clinical Global Impression of Severity (CGI-S) and Change (CGI-C) (Assessor) at each study visit; • DFSS-I (Assessor) at each study visit; • DFSS-S as assessed via subject's diary at each assessment time point; • Patient Global Impression of Severity (PGI-S) and Change (PGI-S) at each study visit; and • Drooling Impact Score (DIS) (Subject) at each study visit.
Duration	
The planned duration of participation for each subject is a minimum of 26 weeks and a maximum of 52 weeks (excluding up to a 21-day screening period), including:
 
 • Up to four 13-week (± 2 weeks) treatment sessions over a 1-year period. Note that Treatment Sessions 3 and 4 are likely, but may not be necessary as the study progresses because the study may be stopped early once enough subjects have completed the study to meet FDA safety database requirements. Any subject that enters the study, however, is required to participate at least through 6 months (i.e., complete Treatment Sessions 1 and 2).
Study Visits	
Screening Period: up to 21 days
 
Treatment Session 1
 
Day 1 (day of injection of study drug) and 4 weeks (± 3 days), 8 weeks (± 3 days), and 13 weeks (± 2 weeks) post-injection, and a telephone follow up 24 hours (± 1 day) post-injection.
 
Treatment Sessions 2, 3, and 4
 
For each 13-week treatment session:

	
 • 4 weeks (± 5 days) and 13 weeks (± 2 weeks) after each treatment, with a telephone follow up 1 week (± 1 day) and 8 weeks (± 5 days) after each treatment. Note that the last visit of a prior treatment session will serve as the first day of the next treatment session.

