During the screening period, the following will be assessed to evaluate the subject's eligibility to participate in the study: inclusion and exclusion criteria; medical, surgical, and medication history; presence or prior history of aspiration, aspiration pneumonia, choking, and/or dysphagia; complete physical exam (including vital signs, height, and weight); neurologic exam; dental exam; clinical laboratory testing; urine pregnancy testing (females of childbearing potential only); and forced vital capacity (FVC) (if warranted, such as in ALS patients). All subjects successfully completing screening will have the following procedures/assessments conducted at baseline (Day 1) before the first injection of MYOBLOC: brief physical exam (including vital signs); FVC (if warranted); neurologic exam; Columbia Suicide Severity Rate Scale (C-SSRS); oral exam; saliva production quantitatively determined via USFR; qualitative assessments by the Investigator including CGI-S and DFSS-I; subject assessments including PGI-S, DFSS, DIS; and urine pregnancy test (result must be negative to proceed with the injection). Those subjects who satisfy all eligibility criteria may receive a dose of MYOBLOC (3,500 Units) via injections into the submandibular and parotid glands on Day 1. Subjects will be contacted by telephone 24 hours post-injection to inquire about their health status.

Subsequent study visits will occur at Weeks 4 (± 3 days), 8 (± 3 days), 13 (± 2 weeks), 17 (± 5 days), 26 (± 2 weeks), 30 (± 5 days), 39 (± 2 weeks), 43 (± 5 days), and 52 (± 2 weeks), with safety and effectiveness assessments made as detailed in the Schedule of Assessments in Table 2 in Section 14.1; telephone follow up will be done at Weeks 14 (± 1 day), 21 (± 5 days), 27 (± 1 day), 34 (± 5 days), 40 (± 1 day), and 47 (± 5 days)

Injections at each treatment session will be done when the subject returns to baseline status as determined by the Principal Investigator, with a minimum interval of 11 weeks from the prior injection but no later than 15 weeks from the prior injection. If after the first treatment of 3,500 Units the subject develops intolerable side effects, but still wishes to remain in the

study, the Investigator has the discretion to decrease subsequent doses, but to no less than a total dose of 2,500 Units.

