13.2 Study Drug Administration and Compliance

Subjects will receive single dose injections of MYOBLOC every 13 weeks (± 2 weeks) for a maximum total of 4 treatments. MYOBLOC will be injected first into the submandibular glands (right and then left) followed by the parotid glands (right and then left)

- Total dose of 3,500 Units (0.7 mL) of MYOBLOC with 1,500 Units (0.3 mL) injected into each parotid gland and 250 Units (0.05 mL) injected into each submandibular gland.

Subsequent injections at each treatment session will be done when subjects return to baseline status as determined by the Investigator, with a minimum interval of 11 weeks from the prior injection. Study drug injections should not be administered if an adverse event of dysphagia or dry mouth of moderate to severe severity persists without prior consultation with the Medical Monitor. If the adverse event has not resolved or has not improved to a mild severity by the end of the per protocol window for injections to occur (every 13 ± 2 weeks), the Medical Monitor should be contacted to discuss whether or not the subject should be dosed, discontinued, etc.

If after the first treatment of 3,500 Units the subject develops intolerable side effects, but still wishes to remain in the study, the Investigator has the discretion to decrease subsequent doses, but to no less than a total dose of 2,500 Units. If this does occur, the total dose can therefore be 2,500 Units to 3,500 Units of MYOBLOC. The Investigator must clearly indicate the adjusted dose given. MYOBLOC will be injected first into the submandibular glands (right then left) followed by the parotid glands (right then left) as follows:

- Total dose of 2,500 to 3,500 Units (0.5 mL to 0.7 mL) of MYOBLOC with 1,000 to 1,500 Units (0.2 mL to 0.3 mL) injected equally into each parotid gland and 250 Units (0.05 mL) injected into each submandibular gland.

All MYOBLOC injections will be performed by Investigators who have prior experience or have been appropriately trained with injecting botulinum toxin and such experience/training will be documented in the study records. Injections will be guided by external anatomical landmarks or by external anatomical landmarks with ultrasound-guided confirmation (Appendix A). Sites designated as “ultrasound” sites will perform all their injections with ultrasound-guidance.

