Telephone Follow-up					X (o)		X	

Abbreviations: AE = adverse event, BP = blood pressure, C-SSRS = Columbia Suicide Severity Rating Scale, DFSS = Drooling Frequency and Severity Scale, HIPAA = Health Insurance Portability and Accountability Act, RR = respiration rate, Temp = temperature, USFR = unstimulated salivary flow rate, VAS = visual analog scale, wks = weeks

- (a) All screening and baseline assessments and results must be available before injection of MYOBLOC.
- (b) Telephone follow-up.
- (c) Office visit.
- (d) Office visit. Serves as last visit of current treatment session and first visit of subsequent treatment session. Study drug injection will occur after the 13-week assessments have been completed for the prior treatment session.
- (e) Must be obtained before conducting any study procedure.
- (f) Includes baseline history of aspiration, aspiration pneumonia, choking, and dysphagia.
- (g) Includes 4 bite-wing radiographs or panoramic imaging (if edentulous or if bite-wing x-rays are difficult due to limited teeth). If the subject has no teeth, then the dentist will determine if panoramic imaging is required at any visit after screening.
- (h) Females of childbearing potential only.
- (i) Forced vital capacity will be measured in all subjects with amyotrophic lateral sclerosis and in other subjects if warranted at the discretion of the Investigator.
- (j) When possible, assessments should be done by the same person in a given subject to ensure consistency throughout the study.
- (k) Global measure of effectiveness must be completed before USFR.
- (l) Subject-rated via entry in diary (not during study visit), daily for first 2 weeks after study drug injection and then weekly for remainder of treatment session.
- (m) Subjects will receive injections guided by external anatomical landmarks or by external anatomical landmarks with ultrasound-guided confirmation. Sites designated as “ultrasound” sites will perform all their injections with ultrasound-guidance.
- (n) Subjects will be injected after completion of all assessments and then will be contacted by telephone 24 hours (±1 day) post-injection to inquire about their health status and remind the subject to complete their diary.

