2 STUDY DESIGN

2.2 Description of Trial Design

This is a multi-center study with a single arm to evaluate the long-term safety and effectiveness of repeated doses (MYOBLOC 3,500 Units single-injection treatment) at intervals of every 13 weeks over a maximum possible duration of 1 year in subjects with troublesome sialorrhea. The study population will be comprised of a mixture of patient populations, including subjects with PD-related sialorrhea, subjects with sialorrhea secondary to other non-PD conditions (e.g., cerebral palsy, ALS, stroke, traumatic brain injury) or secondary to oral cancer or medications (e.g., neuroleptics).

After a screening period (up to 21 days), those subjects who satisfy all eligibility criteria will receive single dose injections of 3,500 Units of MYOBLOC at Day 1 and at subsequent intervals of every 13 weeks (+/-2 weeks) for a total of 4 treatments via injections into the submandibular and parotid glands. Repeat injections at each treatment session will be done when subjects return to baseline status as determined by the Investigator, with a minimum of 11 weeks from the prior injection. After the 1st treatment session for which subjects are injected

with 3,500 Units, the Investigator has the discretion to decrease subsequent injection doses, as a result of poor tolerability, but to no less than a total dose of 2,500 Units.

Subjects will undergo safety and effectiveness assessments at Day 1 (1st injection), and Weeks 4, 8, 13 (2nd injection), 17, 26 (3rd injection), 30, 39 (4th injection), 43, and 52. Telephone follow-up will occur at Weeks 14, 21, 27, 34, 40 and 47 to assess how the subject feels after 1 week (± 1 day) of study drug injection, document adverse events as appropriate, document any new medications the subject may be taking and remind the subject to complete their diary.

At each visit, the following efficacy assessments will be collected, when possible by the same assessor for a given subject:

- Unstimulated salivary flow rate (USFR)
- Clinical Global Impression of Severity (CGI-S)
- Clinical Global Impression of Change (CGI-C), except for Day 1
- Drooling Frequency and Severity Scale (DFSS-I) by Investigator
- Drooling Frequency and Severity Scale (DFSS-S) by subject
- Patient Global Impression of Severity (PGI-S)
- Patient Global Impression of Change (PGI-C), except for Day 1
- Drooling Impact Score (DIS) by Subject

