Abbreviations: AE = adverse event, BP = blood pressure, C-SSRS = Columbia Suicide Severity Rating Scale, DFSS = Drooling Frequency and Severity Scale, HIPAA = Health Insurance Portability and Accountability Act, RR = respiration rate, Temp = temperature, USFR = unstimulated salivary flow rate, VAS = visual analog scale, wks = weeks

- (a) All screening and baseline assessments and results must be available before injection of MYOBLOC.
- (b) Telephone follow-up.
- (c) Office visit.
- (d) Office visit. Serves as last visit of current treatment session and first visit of subsequent treatment session. Study drug injection will occur after the 13-week assessments have been completed for the prior treatment session.
- (e) Must be obtained before conducting any study procedure.
- (f) Includes baseline history of aspiration, aspiration pneumonia, choking, and dysphagia.
- (g) Includes 4 bite-wing radiographs or panoramic imaging (if edentulous or if bite-wing x-rays are difficult due to limited teeth). If the subject has no teeth, then the dentist will determine if panoramic imaging is required at any visit after screening.
- (h) Females of childbearing potential only.
- (i) Forced vital capacity will be measured in all subjects with amyotrophic lateral sclerosis and in other subjects if warranted at the discretion of the Investigator.
- (j) When possible, assessments should be done by the same person in a given subject to ensure consistency throughout the study.
- (k) Global measure of effectiveness must be completed before USFR.
- (l) Subject-rated via entry in diary (not during study visit), daily for first 2 weeks after study drug injection and then weekly for remainder of treatment session.
- (m) Subjects will receive injections guided by external anatomical landmarks or by external anatomical landmarks with ultrasound-guided confirmation. Sites designated as "ultrasound" sites will perform all their injections with ultrasound-guidance.
- (n) Subjects will be injected after completion of all assessments and then will be contacted by telephone 24 hours (± 1 day) post-injection to inquire about their health status and remind the subject to complete their diary.
- (o) Telephone follow-up by the study staff will be conducted 1 week (± 1 day) after study drug injection to assess how the subject feels, document adverse events as appropriate, document any new medications the subject may be taking, and remind the subject to complete their diary.

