2.9 Statistical Methods

Unless specified otherwise, SAS® Version 9.4 or higher will be utilized to perform the statistical analyses of efficacy and safety measures.

Per the protocol, subjects who met all eligibility criteria were to receive single dose injections of 3,500 Units of MYOBLOC every 13 weeks (± 2 weeks) over a maximum possible duration of 1 year, for up to a total of 4 treatments via injections into the submandibular and parotid glands. Repeat injections at each treatment session were to be done when subjects returned to baseline status as determined by the Investigator, with a minimum interval of 11 weeks from the prior injection. If after the first treatment of 3,500 Units the subject developed intolerable side effects, but still wished to remain in the study, the Investigator had the discretion to decrease subsequent doses, but to no less than a total dose of 2,500 Units. Since the majority of subjects received 3500 Units, all statistical tables will present results under one treatment group labeled "Any Dose". Additionally, listings will be categorized as L = low dose (1500-2000 U); M = medium dose (2500-3000 U); H = high dose (3500 U).

Categorical variables will be summarized in general using frequencies and percentages, whereas continuous variables will be summarized in general using descriptive statistics of number of observations (n), mean, standard deviation (SD), minimum (Min), median, and maximum (Max).

In both data listings and CRF domain data tabulations, subject ID will consist of site number plus the assigned subject number.

Hypothesis testing, unless otherwise indicated, will be performed at the 5% significance level. All p-values will be rounded to four decimal places; p-values less than 0.001 will be presented as '<0.001' in all tables. All confidence intervals will be two-sided with 95% coverage.

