2.9.1 Effectiveness analysis

As subjects receive multiple single-dose injections, each single-dose injection plus its follow-up period will be considered as a treatment session.

Effectiveness measures obtained over each of the treatment sessions include USFR, CGI-S, CGI-C, DFSS-I, DFSS-S, PGI-S, PGI-C, and DIS at the injection visit (i.e., Day 1, except for CGI-C and PGI-C, and Weeks 13, 26, and 39), 4 weeks post-injection (i.e., Weeks 4, 17, 30, and 43), 8 weeks post-injection (i.e., Week 8, first treatment session only), and 13 weeks post-injection (i.e., Weeks 13, 26, 39, and 52). The injection visit of Day 1 and Weeks 13, 26, and 39 is considered the baseline (or pre-injection), respectively, for each of the consecutive treatment sessions 1 through 4.

For each treatment session, effectiveness analysis of the treatment response will be performed on USFR change from pre-injection, DFSS-I change from pre-injection, and DFSS-S change from pre-injection, CGI-S, CGI-C, PGI-S, PGI-C, and DIS change from pre-injection, at each of the post-injection time points using a t-test.

In addition, the proportion of treatment responders will be reported for the CGI-C and PGI-C at both pre-injection and post-injection time points over each treatment session. Before the analysis, the CGI-C and PGI-C will be dichotomized into 2 categories, with "very much improved" and "much improved" into 1 category and the remaining levels in the other category.

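### The 13-week change in Sessions 1–3 is read at a re-injection visit that may fall at 11–15 weeks and is tied to return to baseline, so it is neither a fixed-time effect nor comparable with Week 52

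*SAP*

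**What the plan says.** SAP 2.9.1 groups four visits under one time point, "13 weeks post-injection (i.e., Weeks 13, 26, 39, and 52", and applies a t-test to the change from pre-injection. SAP 4.4 repeats this for each measure and for the CGI-C and PGI-C responder proportions. The pre-injection value is the one at the injection visit of the same session.

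Three of the four visits have a second role. Footnote (d) of Protocol Table 2 says of the Week 13 and 26 visits: "Serves as last visit of current treatment session and first visit of subsequent treatment session". A parallel footnote covers Week 39. SAP 2.3 fixes the order within the visit: "Study drug injection will occur after the 13-week assessments have been completed for the prior treatment session".

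The timing of re-injection is linked to outcome. Protocol 13.2 states: "Subsequent injections at each treatment session will be done when subjects return to baseline status as determined by the Investigator". SAP 2.9 repeats the rule: "Repeat injections at each treatment session were to be done when subjects returned to baseline status as determined by the Investigator". Protocol Section 10 sets the limits: "with a minimum interval of 11 weeks from the prior injection but no later than 15 weeks from the prior injection".

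No injection follows the fourth visit. SAP 2.2 lists the later visits as "26 (3rd injection), 30, 39 (4th injection), 43, and 52". The supplied SAP text has no visit-window rule, no effectiveness analysis by actual weeks since injection, and no note that Week 52 differs from the other three.

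**The concern.** The secondary objective is to measure how large the response is at intervals after each treatment. A reader will take the 13-week column as the durability result and will look across sessions for loss or gain of effect.

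If the visit is moved within 11 to 15 weeks towards the point where benefit has gone, subjects with a short response are seen early and those with a long response late. The value then describes status when judged ready for re-injection, not effect at 13 weeks. Week 52 is not selected in this way, yet it carries the same label. An apparent difference between Session 4 and Sessions 1–3 could therefore arise with no change in the drug's effect.

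**Working it through.** **The plan's own figure.** The visit window is "13 weeks (± 2 weeks) after each treatment": 13 − 2 = 11 and 13 + 2 = 15 weeks. This matches the limits in Protocol Section 10. The documents give no waning curve, no variability and no share of visits timed by status, so everything on size below rests on assumptions.

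**What the session baseline does.** Let r be the mean residual effect at a re-injection visit, relative to Day 1 (negative = benefit), and r52 the residual at Week 52. Assume that each injection works equally well.

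- Session 1 change = r − 0 = r
- Sessions 2 and 3 change = r − r = 0, however much effect remains and however visits are timed
- Session 4 change = r52 − r, which is 0 if all visits are calendar-timed and non-zero if status timing has pulled r towards zero

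The near-zero change in Sessions 2 and 3 therefore does not depend on status timing.

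**Model A (assumed).** The effect falls linearly from Week 4 to zero at a subject-specific time T ~ N(13, SD). The residual at time t is max(0, (T − t)/(T − 4)). Compare t = 13 with t = T confined to 11–15 weeks.

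| SD of T (weeks) | Residual at fixed 13 weeks | Residual at status-timed visit | Difference |
|---|---|---|---|
| 2 | 0.070 | 0.013 | 0.057 |
| 3 | 0.096 | 0.033 | 0.063 |
| 4 | 0.118 | 0.053 | 0.065 |

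The shift is about 6% of the Week 4 effect.

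**Model B (assumed).** The effect at time t is −1/(1 + exp((t − T)/1.5)) in units of the peak, with half-effect time T ~ N(half-life, 2.5) and independent visit-to-visit fluctuation. A status-timed visit is the first week from 11 to 15 at which the observed effect is within 0.1 of zero or better, and Week 15 at the latest. A calendar-timed visit falls at random in Weeks 11–15. The share of visits that are status-timed is q. The table gives the Session 1 change.

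| Half-life (weeks) | Fluctuation SD | q = 0 | q = 0.25 | q = 0.5 | q = 1 |
|---|---|---|---|---|---|
| 7 | 0 | −0.06 | −0.06 | −0.06 | −0.05 |
| 7 | 0.3 | −0.06 | −0.01 | +0.04 | +0.14 |
| 10 | 0 | −0.22 | −0.19 | −0.17 | −0.12 |
| 10 | 0.3 | −0.22 | −0.16 | −0.09 | +0.04 |
| 13 | 0 | −0.50 | −0.45 | −0.40 | −0.30 |
| 13 | 0.3 | −0.50 | −0.43 | −0.36 | −0.21 |
| 15 | 0 | −0.70 | −0.65 | −0.60 | −0.50 |
| 15 | 0.3 | −0.70 | −0.64 | −0.58 | −0.46 |

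For half-life 10–15 weeks the shift from the q = 0 column runs from 0.03 (0.22 − 0.19; half-life 10, no fluctuation, q = 0.25) to 0.29 (0.50 − 0.21; half-life 13, fluctuation 0.3, q = 1). At q = 0 there is none. With half-life 7 it is negligible without fluctuation. With fluctuation it is not, because visits are then picked on chance poor readings. Sessions 2 and 3 show about 0.00 in every row. With q = 1 and half-life 10–15, Session 4 shows −0.10 to −0.29 although the true effect is the same in all sessions.

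**The Week 52 clock.** Three intervals of 11–15 weeks put the fourth injection at study Weeks 33 to 45. Counted from that injection, as in the Synopsis, the last visit falls 11–15 weeks later, at Weeks 44 to 60. Read as study Week 52 ± 2 weeks, as Protocol Section 10 lists it, the visit could be 50 − 45 = 5 to 54 − 33 = 21 weeks after the injection.

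**The case against.** A reader might infer that the visit date is set because the effect has worn off, so that the 13-week change is certainly biased towards zero. The documents do not support that. Protocol 14.3.2 gives flexibility in scheduling appointments as the reason for the Week 13 window. No clinic visit is scheduled between Week 8 and Week 13 of Session 1, or between 4 and 13 weeks after later injections, so the Investigator has limited means of tracking return to baseline. Many visits may simply follow the calendar. This stands, and it is why the conclusion is worded as possible attenuation.

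A reader might also infer from Model A that Session 4 would look several times better. That would be a ratio of small residual levels, whereas the SAP analyses change from each session's baseline, and Session 4's own baseline (Week 39) is a re-injection visit.

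The SAP plans no test between sessions and analyses each on its own. It also tabulates average and total session duration per subject (SAP 2.9.2, 5.1), lists individual durations, and lists treatment dates (SAP 3.6). Both points are correct. However, the durations are summarised as exposure, not by session, and are not linked to the effectiveness values. The shared label still invites the comparison that no test makes.

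Finally, a reader might see a contradiction between waiting for return to baseline and injecting by 15 weeks. It is better described as a gap: the two conditions apply jointly, and the case that fails the first by Week 15 is not addressed.

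**Conclusion.** The point holds in a limited form. Weeks 13, 26 and 39 are re-injection visits at 11–15 weeks, linked to the Investigator's judgment of return to baseline, and should not be presented as a fixed 13-week effect. Status timing may attenuate the change there. The size cannot be known from the documents; the modelled range runs from nothing to 0.29 of peak effect, depending on the waning curve, the fluctuation between visits and the share of visits timed by status. Two parts need no such assumption about timing: change from a session-specific baseline tends to zero in Sessions 2–3 if each injection works equally well, and Week 52 differs in kind because no injection follows it.

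The change is worth making, but it concerns the secondary objective only. The primary safety objective is unaffected, and the 4-week and 8-week visits are not status-timed, although the 4-week baselines in Sessions 2–4 are.

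**What to change.** In SAP 2.9.1 and 4.4:

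1. Label Weeks 13, 26 and 39 as *at re-injection visit (11–15 weeks)*, and flag subjects who received no further injection there.
2. Tabulate actual weeks since the prior injection at each of these visits and at Week 52.
3. Report the distribution of injection intervals by session.
4. Add change from Day 1 for Sessions 2–4 beside change from the session baseline.
5. Summarise the weekly diary DFSS-S at fixed weeks up to Week 11 of each session, before any re-injection is allowed, as the fixed-time durability measure. Show levels as well as change, because Protocol 14.3.1 makes the Day 1 pre-injection entry a practice one.
6. State that the Week 13, 26 and 39 values are not to be compared with Week 52 as equal 13-week effects.

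Separately, Protocol Section 10 and 13.2 do not say what happens to a subject not back at baseline by 15 weeks. The sponsor must reconcile these passages; which rule applies is for the sponsor to decide.

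Cost: SAP wording and a few tables from dates and diary data already collected. A new case report form item or a time-to-return analysis is not proposed. The SAP is dated July 2018 and already describes observed data, and return times before Week 11 or between sparse visits are not seen. The downside is that the 13-week result can no longer be quoted as a fixed-time effect.
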